#### **Clinical Procedures**

- Obtain medical history.
- Administer risk behavior & sexual history questionnaire (must take place prior to risk reduction counseling).
- Administer questionnaire to assess symptomatic STDs, including genital ulcer disease, vaginal discharge and rectal symptoms.
- Administer questionnaire to assess 3-month history of symptomatic STDs, such as genital ulcer disease, vaginal discharge and rectal symptoms.
- Provide risk reduction counseling.
- Perform genital exam for signs of STDs.

• Collect specimens for STD baseline assessment:

```
> MSM:
⇒ Rectal swab
⇒ urine
> WSM:
⇒ cervical and vaginal swabs
⇒ urine
```

- Collect blood.
- Provide all available test results.
- Treat bacterial STDs, if clinically indicated, or refer for free treatment.
- Supply study drug, instructions, and adherence counseling.

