# 7.2.2 Secondary Endpoints

Consistent with the secondary study objectives, the following secondary endpoints will be assessed:

- Occurrence and frequency of genital ulcers
- Proportion of doses missed by study participants assigned to twice daily acyclovir and twice daily placebo.

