#### 7.6.2 Secondary Analyses

The primary analysis of the treatment effect will be pooled over the two risk groups: MSM and heterosexual women. As a secondary analysis, separate Cox regressions will be used to estimate the relative risk and confidence interval for a treatment effect in the heterosexual women and MSM subgroups.

Adherence will be measured monthly. The analysis of adherence will be structured to allow us to estimate the adherence rate, test for a difference in compliance between the placebo and treatment groups, test for a trend over time in the compliance rate and examine the relationship between adherence and markers of risky sexual behavior. Specifically, a logistic regression with proportion of tablets taken each month as the outcome and treatment group, clustering of missed doses, time on study and markers of risky sexual behavior as predictors, will be used. Since the analysis will involve repeated observations on individuals, robust variance estimates , will be used to evaluate statistical significance and compute confidence intervals. Standard methods for model checking will be used to check the assumption of a linear trend over time in compliance.

The relationship between compliance and risk of incident HIV infection will also be examined. A proportional hazards model with HIV infection as the endpoint and self-reported adherence, subgroup (women versus MSM) and their interaction as covariates (time-dependent in the case of adherence) will be fit to the data from those individuals randomized to acyclovir. If the adherence is related to risky sexual behavior then the relationship between adherence and risk of HIV infection may be found to differ between MSM (where risk of HIV infection is also related to risky sexual behavior) and women (where risk of HIV infection is likely to be less related to the woman's sexual behavior and more related to her partner's behavior).

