A proportional hazards model will be used to evaluate the effect of treatment arm on recurrence of genital ulcers. Since genital ulcers may recur multiple times over the course of follow-up, the model for recurrent events described by Anderson and Gill will be used for this analysis. Individuals will be considered to be not-at-risk for recurrences when they are being actively treated syndromically for herpes due to symptoms. The robust variance formulation described by Lin will be used to adjust the p-values and confidence intervals if multiple recurrences occur in one or more individuals. In addition, survival analysis will be performed with time to first recurrence as the dependent variable.

Through modeling, exploratory analyses will be conducted to assess the relative contribution of suppression of clinical versus subclinical

reactivation using acyclovir. To address this problem, a proportional hazards model will be fitted, with HIV seroincidence as the outcome and i) self-reported presence of genital ulcers within the past 1 month (yes/no, as well as a continuous variable), and ii) self-reported adherence to acyclovir (proportion of doses and days in which both doses were missed) as covariates. Actual use of acyclovir as opposed to randomization assignment will be used for this analysis. The (negative of the) coefficient for lesions in this model will provide a measure of the decrease in risk associated with suppression of clinical lesions. The coefficient for acyclovir will provide a measure of the protective effect of treatment after controlling for the presence of clinical lesions. Presumably, this additional protective effect is related to suppression of subclinical disease.

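### The genital-ulcer models name treatment arm only, so they give up a usually small amount of precision that the ulcer history collected at enrollment could supply

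*Supplement*

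**What the plan says.** Section 7.2.2 lists "Occurrence and frequency of genital ulcers" as a secondary endpoint. Section 7.6.2 specifies its analysis in some detail:

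- **Effect of interest:** "A proportional hazards model will be used to evaluate the effect of treatment arm on recurrence of genital ulcers".
- **Main model:** "the model for recurrent events described by Anderson and Gill", with participants out of the risk set while they receive syndromic herpes treatment.
- **Variance:** "The robust variance formulation described by Lin", if anyone has more than one recurrence.
- **Supplementary analysis:** "In addition, survival analysis will be performed with time to first recurrence as the dependent variable".

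No baseline covariate or stratum is named for either ulcer analysis. Other models in the protocol do name theirs. In the same section the adherence model has "treatment group, clustering of missed doses, time on study and markers of risky sexual behavior as predictors", and the primary HIV analysis in Section 7.6.1 is stratified by risk group.

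At the enrollment visit, Section 5.3 (Clinical Procedures) requires staff to: "Administer questionnaire to assess 3-month history of symptomatic STDs, such as genital ulcer disease, vaginal discharge and rectal symptoms". The item is not restricted to a subgroup. The letters of amendment and clarification memoranda do not change Section 7.6.2, and no separate analysis plan is among the documents.

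**The concern.** Ulcer history over the 3 months before randomization is in effect a baseline value of the endpoint. Eligibility rests on HSV-2 serology (Section 3.1), not on symptoms, so ulcer rates may well differ widely between participants. A baseline value that predicts the outcome normally sharpens the treatment comparison, and here it is already on the form.

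What is at stake is the precision of the ulcer effect. That effect is the randomized check on the suppression assumed in Sections 1.2 and 7.3, where therapy is taken to be 80% to 90% effective. The choice also affects how the first-recurrence hazard ratio is read, because its value depends on whether history is in the model.

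**Working it through.** **The plan's own figures.** The protocol states no ulcer rate, power or precision for this endpoint. Its power figures concern HIV. The main one reproduces: L = [(1.960 + 1.282)/(0.5 × ln 0.51)]² = 92.7, stated as 93. It says nothing about ulcers.

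**Inputs.** From the protocol: 1,410 per arm (Section 7.3), follow-up of up to 18 months (Section 2.3), and an 80% reduction, i.e. rate ratio r = 0.20 (Section 1.2). Assumed: placebo rate λ of 0.2, 0.5 or 1.0 ulcers per year; gamma frailty with variance θ of 1, 3 or 6; history defined as at least one ulcer in the preceding 0.25 year at the placebo rate.

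**Step 1: arm-only precision, recurrent events.** With a constant rate, the Andersen-Gill model with robust variance is equivalent to a log-rate model with sandwich variance. For n per arm and expected counts μ₀ = 1.5λ and μ₁ = 0.2μ₀,

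Var(log rate ratio) = (1/μ₀ + 1/μ₁ + 2θ)/n.

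- λ = 0.5, θ = 3: (1.333 + 6.667 + 6)/1410 = 0.00993, SE 0.0996, z = 1.609/0.0996 = 16.2.
- λ = 1.0, θ = 6: (0.667 + 3.333 + 12)/1410 = 0.01135, SE 0.1065, z = 15.1.
- λ = 0.2, θ = 6 (largest variance on the grid): (3.333 + 16.667 + 12)/1410 = 0.0227, SE 0.151, z = 10.7.

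Power to reject no effect is therefore close to 100% across the grid before any adjustment.

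**Step 2: add yes/no history (simulation, 300 replicates per setting).** The rate ratio stays at about 0.20. Over the whole grid the robust variance falls by about 0.4% to 27% with error-free history. With assumed recall sensitivity of 60% and specificity of 95%, it falls by about 0.1% to 9%.

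| Setting | Arm-only 95% interval | Adjusted, error-free history |
|---|---|---|
| λ = 0.5, θ = 3 | 0.164 to 0.243 | 0.166 to 0.241 |
| λ = 1.0, θ = 6 | 0.162 to 0.246 | 0.167 to 0.239 |

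In the first row the variance cut is 9.5%, dropping to 2.7% with imperfect recall. The second row is the most favourable corner. From the rounded limits, [ln(0.239/0.167)/ln(0.246/0.162)]² = (0.358/0.418)² = 0.74, a cut of about 26%, in line with the 27% upper end.

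**Step 3: wider assumptions.** With λ of 0.5 to 2 per year, θ of 1 to 4, r of 0.2 or 0.5 and 12 or 18 months, yes/no history cut the variance by 1% to 31%. The rate ratio again did not move.

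**Step 4: first recurrence.** Under gamma frailty the population hazard ratio at time t is

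HR(t) = r(1 + θλt)/(1 + θrλt).

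For λ = 1, θ = 2, r = 0.20 it starts at 0.20 and reaches 0.20 × 3/1.4 = 0.43 at 12 months, because the most ulcer-prone placebo participants leave the risk set first. A Cox model averages over that drift. In simulation the arm-only hazard ratio was 0.303, and 0.281 with yes/no history. In the most heterogeneous setting with r = 0.20 (18 months, λ = 2, θ = 4) it was 0.457 against 0.362. History accounts for only part of the heterogeneity, so neither value returns to 0.20. The mean unadjusted z was at least 5 in every setting of Step 3, including those with r = 0.50.

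The simulations ignore loss to follow-up and the not-at-risk periods during episodic treatment.

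**The case against.** The strongest case against raising this has four parts.

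- **The covariate list may be left to an analysis plan.** None is shown, and the protocol does not say that covariates are ruled out. A reader might infer that it does; the text supports only that none is named. But Section 7.6.2 already fixes the model, risk set and variance for ulcers and lists covariates for its other models, so a concrete addition to a stated method is still fair to propose.
- **The arm-only first-recurrence hazard ratio is not wrong.** A reader might infer that leaving out history biases the ulcer effect toward 1. It does not. The main recurrent-events rate ratio is unchanged. Only the supplementary Cox hazard ratio differs, and under randomization its arm-only value is a valid marginal quantity. The adjusted value answers a different, conditional question. This objection stands in full.
- **No conclusion changes.** A reader might also infer that a null HIV result would be misread because suppression looked too weak or uncertain. The intervals above do not show that: 0.164 to 0.243 and 0.166 to 0.241 support the same reading. This stands too.
- **The gain depends on inputs that the protocol does not give.** Ulcer rates, heterogeneity and recall accuracy are all assumed, and imperfect recall cuts the 9.5% gain to 2.7% in a middle setting. This stands as a limit on size. The direction does not change.

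**Conclusion.** The point holds as an optional efficiency improvement. The ulcer models in Section 7.6.2 name treatment arm only, while a baseline measure of the same endpoint is collected at enrollment. The arm-only analyses are valid and have ample power under the planned 80% reduction.

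The cost of omission in the recurrent-events model is a robust variance that could be lower by about 0.4% to 27% with error-free history, or 0.1% to 9% with recall at 60% sensitivity and 95% specificity. Both ranges assume 0.2 to 1.0 ulcers per year and frailty variance of 1 to 6. For first recurrence, the marginal and history-conditional hazard ratios differ by non-collapsibility, so the report should say which one it gives.

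Nothing here extends to the primary HIV analysis. A parallel check there, with 2,900 participants, relative risk 0.51 and a baseline risk score of log-hazard SD 0.5 or 1.0, moved power from 0.89 to 0.88 and from 0.88 to 0.91 over 400 replicates, which is within simulation error.

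**What to change.** In Section 7.6.2, add that the Andersen-Gill model will include 3-month genital ulcer history from the enrollment questionnaire (yes, no, missing) as a baseline covariate, with the robust variance kept and the unadjusted estimate reported beside the adjusted one. For time to first recurrence, state that the unadjusted and history-adjusted hazard ratios will both be reported, the second labelled as conditional on history. The choice should be fixed before unblinding. If a separate analysis plan exists, it should carry the same wording.

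The cost is a sentence or two of analysis text and no new data collection. The small downsides are the handling of a few missing answers and the conditional reading of the adjusted first-recurrence hazard ratio.

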### 7.7 Interim Efficacy Analysis

An independent Data Safety and Monitoring Board (DSMB) will be convened for this study. The DSMB will meet approximately every six months throughout the study. The primary responsibilities of the DSMB are to 1) periodically review and evaluate the accumulated study data for participant safety, study conduct and progress, and efficacy, and 2) make recommendations to the study investigators and DAIDS concerning the continuation, modification, or termination of the trial. The DSMB will consider study-specific data as well as relevant background knowledge about the disease, test agent, and/or patient population under study.

Analyses presented to the DSMB will include comparability of acyclovir and placebo groups at enrollment, compliance with the intervention, loss to follow-up rates, adverse event reports, and HIV incidence by treatment arm. Based on these analyses, the DSMB will make recommendations on whether to continue or halt the study. The study will be halted if the seroincidence of HIV is statistically significantly lower in the acyclovir group than in the placebo group, i.e., that effectiveness of acyclovir has been demonstrated. An O-Brien-Fleming stopping rule will be used to control the overall type I error rate of the study and provide guidance to the DSMB. The DSMB will also recommend halting the study if the HIV seroincidence among acyclovir users is higher than placebo users to the extent that the hypothesis of protective efficacy of acyclovir is very unlikely. The DSMB will make recommendations regarding adjustment of sample size, as required, if HIV incidence or follow-up rates are different than anticipated.

HIV seroincidence and safety results by randomization group will be available only to DSMB members and not to the research investigators until the trial is completed.

Further information about the DSMB is contained in a separate DSMB charter.

## 8 HUMAN SUBJECTS CONSIDERATIONS

#### 8.1 Ethical Review

This protocol and the template informed consent forms contained in Appendices IV-IX — and any subsequent modifications — will be reviewed and approved by DAIDS Prevention Science Review Committee with respect to scientific content and compliance with applicable research and human subjects regulations.

The protocol, site-specific informed consent form, participant education and recruitment materials, and other requested documents — and any subsequent modifications —will be reviewed and approved by the ethical review bodies responsible for oversight of research conducted at the study site.

Subsequent to initial review and approval, the responsible local Institutional Review Boards/Ethical Committees (IRBs/ECs) will review the protocol at least annually. The Investigator will make safety and progress reports to the IRBs/ECs at least annually, and within three months of study termination or completion. These reports will include the total number of participants enrolled in the study, the number of participants who completed the study, all changes in the research activity, and all unanticipated problems involving risks to human subjects or others.

In addition, the results of all DSMB reviews of the study will be provided to the IRBs/ ECs.

### 8.2 Informed Consent

Written informed consent will be obtained from each study participant. Each study site is responsible for developing study informed consent forms for local use, one for study screening and one for enrollment, based on the templates in Appendices IV/V and VII/VIII, that describe the purpose of the screening and the study, the procedures to be followed, and the risks and benefits of participation, in accordance with all applicable local and US regulations. An additional informed consent document will be developed for storage and future use of blood based on the template in Appendix VI, and an additional informed consent will be developed to include the new HIPAA regulations (Appendix IX, US sites only). The study site is responsible for translating the template forms into local languages, and verifying the accuracy of the translation by performing an independent back-translation.

Before documenting their informed consent, participants will be given the opportunity to ask questions until they fully understand the study. They will be told that they can return at any time to obtain more information or have further questions answered. Participants will be offered a copy of their informed consent forms. Study staff will document the informed consent process as instructed in the study-specific procedures manual.

### 8.3 Risks

Acyclovir has been extensively evaluated for toxicity and found to be a very safe drug. The only AEs associated with this acyclovir regimen are nausea and vomiting (0.4-11.3% vs 0.2-14.0% on placebo), diarrhea (1.0-3.6% vs. 0.3-2.9%), or headaches (0-7.4% vs. 0-9.5%) as observed in more than 7500 clinical trial patients who received acyclovir in doses ranging from 0.2-4.0 grams per day. Serious AEs have not been observed.

Venipuncture is sometimes associated with discomfort during phlebotomy, dizziness, and rarely, an infection at the site of phlebotomy. Examination and swabbing of genital lesions can also be associated with discomfort. Participants may become embarrassed, worried, or anxious when completing their HIV risk assessment and/or receiving HIV counseling. They also may become worried or anxious while waiting for their HIV and HSV-2 test results. Trained counselors will be available to help participants deal with these feelings. Individuals who learn that they have HSV-2 or HIV infection, may experience anxiety or depression related to their test results.

Although study sites will make every effort to protect participant privacy and confidentiality, it is possible that participants' involvement in the study could become known to others, and that social harms may result (i.e., because participants could become known as participating in a trial of HSV-infected individuals or at "high risk" for HIV infection). For example, participants could be treated unfairly or discriminated against, or could have problems being accepted by their families and/or communities.

### 8.4 Benefits

Participants randomized to acyclovir may experience fewer anogenital ulcers during therapy with the study drug. Regardless of randomization arm, participants will be offered (at the discretion of the Investigator or designee) acyclovir 400 mg tid for 5 days during episodes of genital herpes identified during the study.

In addition, participants will receive HIV and STD counseling, testing, and genital exams in this study, as well as STD treatment. They will learn how to protect themselves from becoming infected with HIV and other STDs. They will also be referred for further counseling and treatment, if applicable. Participants will be provided with male condoms throughout the study.

There may be no direct benefits to participants in this study. However, participants and others may benefit in the future from information learned from this study. Specifically, information learned in this study may lead to use of HSV-2 suppressive therapy to prevent sexual transmission of HIV.

#### 8.5 Access To HIV-Related Care

#### 8.5.1 Counseling

All risk-reduction and pre-test counseling will take place after behavioral data collection. At each visit, the health educator/counselor will provide the study participant with information on methods of HIV transmission and prevention, use of condoms, and pre- and post test HIV counseling, if applicable.

HIV pre-test, risk reduction, and post-test counseling will be provided to all potential study participants who consent to undergo HIV screening to determine their eligibility for this study, and to all enrolled participants at each follow-up HIV testing timepoint. Counseling will be provided in accordance with local standards of practice at each study site. In accordance with the policies of the US National Institutes of Health, participants must receive their HIV test results in order to take part in this study. The study site will document its counseling policies and procedures prior to study implementation for purposes of staff training and study monitoring.

#### 8.5.2 Care For Participants Identified As HIV-Infected

This study will identify persons who are infected with HIV, either as part of the study screening process or during follow-up of enrolled participants. The enrollment blood sample will be tested at the Central Laboratory via PCR technique to determine whether participants who seroconvert at their first HIV test after enrollment were HIV positive at the enrollment visit; this test result should be communicated to the participant(s). Study staff will provide participants with their HIV test results in the context of posttest counseling. They also will refer persons found to be HIV-infected to available sources of medical and psychosocial care and support, as well as to any available research studies for HIV-infected persons. Individuals who become HIV-infected during the trial will be referred to local providers for HIV-specific care. In addition, protocol team members will work with the health ministries of study countries to determine means of increasing the subsequent availability of acyclovir. Lastly, participants who become HIV-infected while they are in the study will be offered enrollment into a six-month ancillary study to assess affect of HSV-2 suppression on HIV-1 levels in the first six months after

infection ("viral set-point") through a separate protocol, Informed Consent Forms, and maintenance of the initial treatment randomization . Participants will cease to have study visits for the HPTN 039 main study protocol and no further data will be collected from them for this protocol

once their HIV-infection has been confirmed.

## 8.6 Participant Reimbursement

Participants will be compensated for their time and effort in this study, and/or be reimbursed for travel to study visits and time away from work. Site-specific reimbursement amounts will be specified in the study informed consent form, and approved by the IRB/ECs.

# 8.7 Confidentiality

All study-related information will be stored securely at the study sites. All participant information will be stored in locked file cabinets and/or in lockable areas with access limited to study staff. All laboratory specimens, reports, study data collection, process, and administrative forms will be identified by a coded number only to maintain participant confidentiality. All records that contain names or other personal identifiers, such as locator forms and informed consent forms, will be stored separately from study records identified by code number. All local databases will be secured with password-protected access systems. Forms, lists, logbooks, appointment books, and any other listings that link participant ID numbers to other identifying information will be stored in a separate, locked file in an area with limited access.

Participant's study information will not be released without the written permission of the participant, except as necessary for monitoring by the NIAID and/or its contractors; representatives of the HPTN CORE, SDMC, and/or CL; the US Food and Drug Administration, and/or other government and regulatory authorities.

US Sites only: All Protected Health Information (PHI) will be protected according to the provisions of the Health Insurance Portability and Accountability Act and will only be used or disclosed as allowed by the Privacy Rule pursuant to relevant waivers, authorizations or as required by Federal law.

